- 11.2.2 PRIMARY EFFICACY OBJECTIVE: For the low-risk cohort, the study is powered to compare 5-year bDFS rates observed with CyberKnife to 5-year bDFS rates reported with dose-escalated external beam RT. In Beaumont's monotherapy HDR series treating LR patients, 5-yr ASTRO bDFS was 98%; in Demanes' series of 75% LR and 25% IR, this was 96%. We would expect Phoenix outcomes to be slightly higher than ASTRO outcomes at 5 years. Since CK delivers doses similar to HDR monotherapy, a conservative estimate of the success rate for CK is 97.5% for LR patients. In LR patients, prospective studies from Memorial Sloan Kettering⁷⁶ (203 patients, 81Gy) and MD Anderson⁷⁷ (32 patients, 78Gy) demonstrated 5-vr bDFS (Phoenix definition) of 92% and 93%, respectively. Thames' 9-institution review of 231 dose-escalated (70-76Gy) LR patients reported 94% 5-yr Phoenix bDFS. Thus, an objective performance criteria (OPC) for lowrisk patients treated with dose-escalated external beam RT is 93% 5-yr bDFS. Assuming the CK success rate is 97.5%, to test superiority of CK against this OPC with 80% power at the 1-sided 5% significance level will require 150 patients. Increasing the sample size by 1/(0.92*0.92) for ineligible/lack-of-data cases yields 177.22; the required sample size for low-risk patients is 178 patients.
- 11.2.3 TOTAL AND RELATIVE ENROLLMENT OF RISK GROUPS: Per sections 11.2.1 11.2.2, enrollment of 178 low-risk patients are required to compare the 5-year bDFS rate observed with CyberKnife to the 5-year OPC rate, and 120 intermediate risk patients are required to establish acceptable toxicity for each risk cohort. CaPSURE data showed a ratio of low to intermediate risk patients, using D'Amico's definition⁷⁸, of 46.8%:37.2%. This CK protocol excludes intermediate risk patients with both PSA 10-20ng/ml and Gleason 7 histology. Based on proportions of patients in these subgroups reported in Partin's⁷⁹ study, this would exclude 12% of intermediate risk patients. Combining these proportions, we would expect a ratio of low to intermediate risk patients of 1.43: 1. Thus we would expect 172 low-risk patients enrolled by the time 120 intermediate risk patients have been enrolled. Each cohort will be closed to accrual once requisite enrollment is achieved: 178 low-risk patients, and 120 intermediate risk (298 total patients)

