- 11.2.4 ACCRUAL RATE: the initial three months while institutions are obtaining IRB approval, therefore we do not expect to meet the targeted monthly accrual rate until after the first three months. The estimated accrual rate is 2.5 patients per study site per month. Expectations of 10 treating study sites assume an accrual period of approximately 11 months, or 14 month total
- 11.2.5 INTERIM ADJUSTEMENT IN ENROLLMENT: Interim analysis of the first 200 enrolled patients showed that 13 were actually ineligible because they were taking finasteride or dutasteride. Enrollment will thus be increased by 13 patients. Exclusion of patients on 5-alpha reductase inhibitors is clarified in section 5.12. We recognize that LHRH agonist/antagonist (e.g. leuprolide, goserelin, triptorelin, degarelix), hormone (e.g. DES), or peripheral blocker (e.g. flutamide, bicalutamide, nilutamide) administration given more than two months before enrollment may impact efficacy. Thus sample size (section 11.2) will be increased to insure enrollment is sufficient to achieve study objectives for the subgroup of patients naïve to such therapy. Interim analysis of the first 200 enrolled patients showed

 \Box

four had received LHRH agonists or peripheral hormone blockers. We could expect four more such patients to be enrolled through completion of the study. Thus enrollment should be increased by an additional eight patients, or 21 patients total. Applying the proportion of low to intermediate risk patients described in section 11.2.3, total enrollment will be increased to 129 intermediate-risk, and 190 low-risk (319 patient total). If subsequent interim evaluations show the estimated proportion of ineligible/lack-of-data cases is inaccurate, required enrollment will be accordingly adjusted.

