11.3 INTERIM ANALYIS FOR FUTILITY

When at least 50% of the Low Risk subjects have reached the 3 year time point, an interim analysis will be performed for the primary efficacy hypothesis to determine if it is futile to continue with study follow-up through 5 years. The primary efficacy study objective is to establish with 95% confidence that the 5 year bDFS rate is >93% (the OPC). For the interim analysis the 3 year bDFS rate will be used along with the same OPC of 93%.

11.3 1. Methodology:

The determination of 3 year bDFS will be made for all subjects with sufficient data through 3 years. Next, the probability of meeting the efficacy object at 3 years will be determined using simulation. Results for the subjects w/o sufficient data through 3 years will be simulated using a binomial distribution. The assumed probability of success (i.e. bDFS) will be set at the rate that was observed for the subjects w/ 3 year data. The simulation will be run 1,000 times resulting in 1,000 complete datasets. The lower confidence interval limit for 3 year bDFS rate will be calculated, using the Wilson method, for each dataset, and probability of success will be the proportion of datasets where the lower confidence limit is below 93%.

11.3.2.Rule:

If the probability of having a successful study is less than found to be less than 20% then it will be considered futile to continue with follow-up through 5 years.

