11.4 STATISTICAL METHODS

11.4.1 PRIMARY ENPOINTS

11.4.1.1 SAFETY: The upper limit of a one-sided 95% confidence interval for the expected proportion of patients experiencing a Serious Adverse Event (SAE) is estimated by U, where

$$U = \frac{(2np + Z_{0.05}^2) + Z_{0.05}\sqrt{Z_{0.05}^2 + 4pn(1 \cdot p)}}{2(n + Z_{0.05}^2)}$$

Here "p" is the observed proportion of patients experiencing an SAE . The CyberKnife intervention will be considered to be safe if this study's result verifies that U is not above $20\%^{80}$.

11.4.1.2 EFFICACY: The lower limit of a one-sided 95% confidence interval for the expected proportion of patients experiencing biochemical disease-free survival (bDFS) is estimated by L, where

$$L = \frac{(2np + Z_{0.05}^2) \cdot Z_{0.05} \sqrt{Z_{0.05}^2 + 4pn(1 \cdot p)}}{2(n + Z_{0.05}^2)}$$

Here "p" is the observed proportion of patients experiencing bDFS in either

ACCP001.4

arm of the trial. The CyberKnife intervention will be considered to be effective if this study's result verifies that L is not below 93%.

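### The 93% efficacy rule in 11.4.1.2 covers either arm, but 11.2.2 derives 93% for low-risk men only, on the Phoenix definition

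*Combined protocol and SAP*

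**What the plan says.** Section 11.4.1.2 gives a Wilson lower limit L in which p "is the observed proportion of patients experiencing bDFS in either" "arm of the trial. The CyberKnife intervention will be considered to be effective if" L is not below 93%. It names no cohort and no PSA definition.

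Section 12.5 also speaks of either arm of the trial. Its table shows that the arms are the low-risk and intermediate-risk cohorts, each judged independently.

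The source of the 93% is 11.2.2: "For the low-risk cohort, the study is powered to compare 5-year bDFS rates observed with CyberKnife" with published external-beam results. From three low-risk series on the Phoenix definition (92%, 93% and 94%) it concludes that "an objective performance criteria (OPC) for lowrisk patients treated with dose-escalated external beam RT is 93% 5-yr bDFS". The expected rate of 97.5% is also for low-risk men.

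On the other cohort, 11.2.3 says that "120 intermediate risk patients are required to establish acceptable toxicity for each risk cohort". Under 11.2.5, "total enrollment will be increased to 129 intermediate-risk, and 190 low-risk". The futility look in 11.3 takes place "When at least 50% of the Low Risk subjects have reached the 3 year time point".

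Section 2.0 lists both the Phoenix and ASTRO definitions under the primary efficacy goal, and names no cohort for it.

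**The concern.** The decision rule reaches further than its derivation. In the protocol's own vocabulary, either arm includes intermediate-risk men. For them the documents give no benchmark, no expected 5-year bDFS and no efficacy sample size. An analyst who follows 11.4.1.2 literally would issue a formal verdict on that cohort against a figure that belongs to another population. The result could be an unsupported finding that treatment is not effective, or a pass against the wrong comparator.

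The word either is itself ambiguous. It may mean each arm separately, or that one passing arm is enough. The second reading gives the study-level claim two chances of success.

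A smaller gap is the missing PSA definition. The benchmark is Phoenix-based, but section 2.0 gives Phoenix and ASTRO equal standing, so the rule leaves room to choose once the data are seen.

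**Working it through.** **1. The plan's own figure (11.2.2).** Null rate 0.93, alternative 0.975, one-sided 5%, 80% power:

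n = [1.645·√(0.93·0.07) + 0.842·√(0.975·0.025)]² / 0.045² = (0.4197 + 0.1314)² / 0.002025 = 149.97, so 150.

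With the plan's loss factor, 150/0.92² = 177.22, so 178. Both figures reproduce. The patient-weighted mean of the three benchmark series is (203·92 + 32·93 + 231·94)/466 = 93.06%, which agrees with 93%.

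**2. The rule in the cohort it was built for.** With x men free of failure out of n, p = x/n and z = 1.645:

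L = [2np + z² − z·√(z² + 4np(1−p))] / [2(n + z²)]; pass if L ≥ 0.93.

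At n = 150, L is 0.9331 with 5 failures and 0.9245 with 6, so at most 5 are allowed. Exact binomial probabilities of passing are 4.5% at a true 93% and 82.5% at 97.5%.

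**3. The same rule in intermediate-risk men.** Evaluable n has to be projected:
- 101: the planned number, 120·0.92² = 101.6. It is also what remains of 129 if the 9 men added by 11.2.5 only replace known exclusions: (129 − 9)·0.8464 = 101.6.
- 109: 129·0.8464 = 109.2.
- 120 and 129: the planned and amended enrolment with no loss, as upper cases.

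The documents give no intermediate-risk rate, so the true rates below are assumptions.

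| n | Failures allowed | L at that count | L with one more | Pass if true 90% | 95% | 97.5% |
|---|---|---|---|---|---|---|
| 101 | 2 | 0.9419 | 0.9280 | 0.2% | 11% | 54% |
| 109 | 3 | 0.9331 | 0.9207 | 0.4% | 20% | 71% |
| 120 | 3 | 0.9391 | 0.9278 | 0.2% | 14% | 65% |
| 129 | 4 | 0.9327 | 0.9225 | 0.3% | 22% | 78% |

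The allowance steps up at n = 104 and n = 124, so the pass probability moves in jumps. Over every n from 101 to 129 it runs from 0.1% to 0.6% at a true 90%, 11% to 25% at 95%, and 52% to 80% at 97.5%. An even chance of passing needs a true rate of 96.2% (n = 124) to 97.4% (n = 103). An 80% chance needs 97.5% to 98.5%.

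**4. If one passing arm is enough.** Suppose both true rates are 93%. The chance that at least one arm passes is 1 − (1 − 0.0448)(1 − 0.0244) = 6.8% at n = 150 and 101. At n = 190 and 129 it is 1 − (1 − 0.0408)(1 − 0.0481) = 8.7%. The nominal level is 5%.

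**5. PSA definition.** The brachytherapy rates behind the 97.5% are on ASTRO ("monotherapy HDR series treating LR patients, 5-yr ASTRO bDFS was 98"% in one, 96% in the other). If low-risk ASTRO data were judged against the Phoenix-based 93% at n = 150, power would be 44% at a true 96%, 70% at 97% (the Table 1 average) and 92% at 98%, against the planned 82.5%. The direction of the gap between definitions is not uniform: one LDR row of Table 1 has ASTRO at 88% and Phoenix at 86%.

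**The case against.** The strongest reply is that the intent is clear. Section 11.2.2 opens with the low-risk cohort and powers only that cohort, 11.2.3 assigns the intermediate-risk number to toxicity, and 11.3 times its look at the efficacy hypothesis on low-risk follow-up. On this view either arm is a drafting slip. The rule also gives one conclusion about CyberKnife and mentions no separate cohort verdict. As for the definition, the benchmark is Phoenix and 9.4.1 keeps ASTRO for comparison with earlier literature.

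Much of this stands. A slip is quite likely, and the documents do point to Phoenix. But 11.4.1.2 is the text that decides the trial, and it says something else. Section 11.3 uses low-risk follow-up to set the timing, and does not restate whose data enter the final rule.

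Two points about size are also fair. The plan's own logic favours about 101 evaluable intermediate-risk men; 120 and 129 assume no losses at all. The pass probabilities rest on assumed true rates, so they show that the cohort is not powered for this rule and do not predict its result.

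**Conclusion.** The rule is wrong as written. It applies a low-risk, Phoenix-based benchmark to a cohort that has no benchmark and was not sized for efficacy. If either means each arm, the intermediate-risk cohort is more likely to fail than pass unless its true 5-year bDFS exceeds about 96.2% to 97.4%, depending on evaluable n. At the planned n = 101, even the low-risk target of 97.5% gives only a 54% chance of passing.

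The low-risk test, taken alone, keeps its error rate and power. Only the reading in which one passing arm suffices inflates error, to between 6.8% and 8.7% for the study-level claim. The wording does not settle which reading applies. The missing PSA definition is a lesser matter, since the documents already lean to Phoenix. The change should be made, but it is a correction of scope and leaves the design as it is.

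**What to change.** In 11.4.1.2, define p as the observed 5-year bDFS proportion in the low-risk cohort, Phoenix definition. Add a matching line to the primary efficacy goal in 2.0. Report intermediate-risk bDFS, and ASTRO bDFS in both cohorts, as estimates with confidence intervals and no pass or fail against 93%.

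If the sponsor does want an intermediate-risk verdict, it needs its own justified benchmark and sample size, fixed before the 5-year data are read.

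The cost is one sentence and one line. The low-risk calculation of 150 evaluable and 178 enrolled is unchanged. All that is given up is an intermediate-risk efficacy claim that was never powered.

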11.4.2 SECONDARY ENDPOINTS

- 11.4.2.1 QUALITY OF LIFE ASSESSMENTS: The SF-12 scores. AUA score, EPIC-26 scores are used to quantify quality of life (QoL) at baseline and repeatedly during the post treatment period (see Section 9.0). We will use the generalized estimating equation (GEE) method to provide valid inferences. This method was originated to make inference about average behaviour, where the dependent variable depends not only on the "explanatory" variable (time measured in months) but also on the correlation of a patient's repeated measurements. The GEE approach fits the model to the observed data as closely as possible, weighting each patients' "cluster" of measurements over time inversely to its variance – covariance matrix. With this method, no imputations are required and all data recorded is use in the analysis. Other important features of GEE are that no distributional assumptions for the dependent variable are required to use the method and in most cases valid inferences are provided even when the correlation structure is miss-specified. For each score, we will use GEE to fit a model to patients' longitudinal course of repeated values. We hypothesize that immediately following treatment, the GU & GI subsections of the EPIC-26 and the AUA will demonstrate a worsening of GU and GI function, but this will return to normal with time. We further hypothesize that the sexual function subset of the EPIC-26 will show gradual worsening function relative to baseline over the five-year follow-up period. These QOL outcomes will be compared to those reported in other prospective studies using the same instruments, including RTOG 0232 and 0415
- 11.4.2.2 ADVERSE EVENTS: All adverse events will be recorded on the case report forms. For both acute (<=90 days of treatment start) and late (>90 days of treatment start), the frequency and proportion of each type of adverse event will be presented in tabular form, on both a per-patient and a per-event basis.
- 11.4.2.3 SURVIVAL OUTCOMES: "Survival" analyses will be performed for the outcomes defined in Section 9.4. These include Local and Distant tumor Control, Disease-free survival for measures listed in Section 9.4.3.2, Disease-specific survival for measures including those listed in Section 9.4.3.3, and Over-all survival for death from any cause. Periodically over the extended follow-up period, Kaplan-Meier "survival" curves will be calculated (examples: at 6 months, yearly, 5 years, at end of patient follow-up). From the Kaplan-Meier curve, descriptive statistics will be calculated including estimates of survival rates and mean and quartile survival times.
- 11.4.2.4 WORK EFFORT: At each site and for each patient, time spent actively involved with planning and treatment shall be recorded for all member of the treatment team (therapist, physicist, radiation oncologist, and urologist). The required on-site supervisory time will also be recorded. Average times will be recorded. Time spent by team members will be compared and correlated with other outcomes (e.g. experience level of team member, patient enrollment, treatment planning/delivery QA outcomes,

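### The quality-of-life GEE is called valid without a missing-data assumption, a named working correlation or a stated form for time

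*Combined protocol and SAP*

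**What the plan says.** Section 11.4.2.1 of the protocol covers the quality-of-life scores.

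- **Method and claim:** "We will use the generalized estimating equation (GEE) method to provide valid inferences".
- **Missing data:** "With this method, no imputations are required and all data recorded is use in the analysis".
- **Correlation:** "in most cases valid inferences are provided even when the correlation structure is miss-specified". The text describes weighting each patient's measurements by the inverse of their covariance, but names no working structure.
- **Covariate:** the only explanatory item is the "variable (time measured in months"). Whether it enters as a line, a curve or a set of visit categories is not said.
- **Urinary and bowel hypothesis:** the plan expects an early decline in these domains, followed by recovery, of which it says "but this will return to normal with time". No visit or contrast defines recovery.
- **Sexual function hypothesis:** the EPIC-26 subset "will show gradual worsening function relative to baseline over the five-year follow-up period".

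Results are then to be compared with RTOG 0232 and 0415. Neither this section nor any other states a missing-data assumption for these scores or a sensitivity analysis. The 8% allowance for ineligible or lack-of-data cases in 11.2.1 serves the sample size only.

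**The concern.** The robustness of unweighted GEE to a wrong correlation structure is a result about complete data, or data missing for reasons unrelated to the scores. It does not carry over to dropout that depends on the scores. The plan relies on that robustness and on using no imputation, without naming the condition that joins the two.

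Three features make this relevant here. Questionnaires run for five years. Section 14.7 says withdrawn patients may be asked to continue PSA tests and exams but does not mention questionnaires, so these data may stop at withdrawal. The trial has one treatment and an external comparison, so there is no concurrent arm in which dropout bias could partly cancel.

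If men who are doing badly return fewer forms, the remaining averages can look too good. That is the direction of the benefits listed in 14.6 (less urinary, bowel and sexual toxicity than other treatments). Separately, if months were entered as a single slope, the model could not represent the urinary and bowel hypothesis.

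**Working it through.** The documents give no SD, correlation, effect size or dropout rate for these scores, so there is no stated figure to reproduce. Only the visit times come from the plan (EPIC-26 at baseline, 1, 6 and 12 months, then yearly to 60 months; section 9.0 table and 9.1.4). Every other value below is assumed.

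**1. When the claim holds.** GEE solves Σ Dᵢ′Vᵢ⁻¹(Yᵢ − μᵢ) = 0 over the observed scores.
- Dropout unrelated to scores: every observed residual has mean zero, so any V gives a consistent estimate.
- Dropout dependent on earlier observed scores: the observed residuals no longer have mean zero. With an identity link, the weighted sum generally returns to zero only if V is the true covariance.
- Dropout dependent on the unseen current score: the residual is shifted even given the history, and no V removes the shift.

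**2. Size.** Simulation settings: 298 men (the total in 11.2.3, before the increase to 319 in 11.2.5), SD 15, within-man correlation 0.6, visit as a category, true 5-year change 0, higher score better, 150 replicates. The log-odds of dropout at each visit are −2.9 + s × (SDs below the visit mean). Between 60% and 69% of men were retained at five years. Entries are the bias in 5-year change, with 95% CI coverage in brackets.

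| True correlation | Dropout depends on | s | Independence GEE | Exchangeable GEE |
|---|---|---|---|---|
| Exchangeable | nothing | 0 | −0.11 (94%) | −0.02 (95%) |
| Exchangeable | previous score | 0.5 | +1.60 (69%) | −0.03 (95%) |
| Exchangeable | previous score | 1 | +3.64 (7%) | +0.15 (93%) |
| Exchangeable | unseen score | 0.5 | +1.83 (56%) | +0.47 (94%) |
| Exchangeable | unseen score | 1 | +4.06 (3%) | +1.28 (70%) |
| Autoregressive | nothing | 0 | +0.08 (90%) | +0.12 (91%) |
| Autoregressive | previous score | 0.5 | +0.51 (93%) | −0.44 (93%) |
| Autoregressive | previous score | 1 | +1.37 (85%) | −0.72 (91%) |
| Autoregressive | unseen score | 0.5 | +0.92 (89%) | +0.36 (95%) |
| Autoregressive | unseen score | 1 | +2.26 (61%) | +1.12 (87%) |

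The rows with dropout unrelated to scores show the simulation noise, about 0.1 point.

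A second simulation on similar assumed values (300 men, SD 15, 63-69% retained, dropout on the previous score) gave these ranges of bias:
- independence GEE: +1.3 to +3.3
- exchangeable GEE: −0.75 to +0.07
- likelihood model with unstructured covariance: −0.15 to +0.09

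**3. A mixed model is not automatically better.** With 319 men, six annual visits, SD 25, correlation 0.6, a true change of −15 and dropout slopes of 0.3, 0.5 and 0.8 per SD, the estimates were:
- independence GEE: −13.4, −12.5, −10.3
- exchangeable GEE: −14.8, −15.1, −14.8
- random-intercept mixed model: −14.8, −15.2, −14.9

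The last two agree within about 0.1 point. Under a true autoregressive correlation both miss by a similar amount (for example −16.1 and −16.2).

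**4. Form of time.** Take an assumed EPIC change of 0, −10, −4, −2, 0, 0, 0, 0 at months 0, 1, 6, 12, 24, 36, 48, 60.
- Mean month = 187/8 = 23.375. Mean change = −16/8 = −2.
- Sxx = 7957 − 187²/8 = 3585.875. Sxy = −58 + 8 × 23.375 × 2 = 316.
- Slope = 316/3585.875 = 0.088 per month. Intercept = −2 − 0.088 × 23.375 ≈ −4.06.
- Fitted value at month 1 = −3.97, a rise of 0.09 where the assumed truth falls by 10.
- Fitted change over 60 months = 60 × 0.0881 ≈ +5.3 where the assumed truth is 0.

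Visit categories reproduce the assumed curve exactly.

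**The case against.** The strongest reply is that the plan describes inverse-covariance weighting, which points away from independence. Exchangeable weighting kept the bias under 1 point when dropout depended on earlier scores, and near zero when that structure was right. Where it was wrong the bias was negative, which exaggerates decline instead of hiding it. All of this stands. A reader might infer that GEE is valid only when dropout is unrelated to the scores, or that the planned analysis is biased by 1 to 3 points. The documents support neither, because the independence results describe a weighting the plan does not adopt.

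A reader might also infer that the plan fits one straight line in months. It does not say so. Months appears in a general description of GEE, and categories or a curve are not excluded. A linear trend could even suit the sexual-function hypothesis. The gap is an unstated form, not a demonstrated misfit.

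The no-imputation sentence is literally true of fitting the model, and the correlation claim is hedged. What remains is that the stated aim is valid inference, and with a working structure that is unnamed and allowed to be wrong, the reader cannot tell whether the protection applies. Exchangeable weighting also left +0.4 to +1.3 points when dropout depended on unseen scores.

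**Conclusion.** The concern holds as a gap in specification. The plan claims validity with no imputation and tolerates a wrong correlation structure. Under score-dependent dropout those two assurances do not hold together in general.

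On the assumed values, dropout on the previous score gave a bias of roughly +1 to +3 points with independence weighting (+0.5 to +3.6 across all settings run) and under 1 point in either direction with exchangeable weighting. The size depends on the assumed SD, correlation and 31-40% loss by year five, and on a working structure the plan leaves open, so no single figure can be given for the planned analysis. The linear-time result is conditional in the same way.

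Quality of life is a secondary objective with no success criterion or power statement. The primary safety and bDFS conclusions in 11.4.1 do not change.

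**What to change.** In section 11.4.2.1:

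1. Enter visit as a categorical factor, estimate the change from baseline at each visit, and say which of these estimates addresses recovery.
2. Make the main model a likelihood-based repeated-measures model with unstructured covariance (not a random intercept alone, which behaved like exchangeable GEE), or a GEE weighted by the inverse probability of remaining under observation.
3. State that this model assumes dropout depends only on observed scores.
4. Delete the assurance that no imputation is needed for valid inference.
5. Add one sensitivity analysis in which missing scores are set worse than the model predicts, since neither main model handles dropout on unseen scores.

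The cost is SAP wording, routine software and a little more analysis work. The likelihood model brings a normality assumption for bounded scores, which GEE avoids and which should be checked. No extra patients or visits are needed.

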2.0 OBJECTIVES

PRIMARY OBJECTIVES: The primary safety goal of this study is to estimate, in both low-risk and intermediate-risk cohorts, the rates of acute and late grade 3-5 gastrointestinal and genitourinary toxicity observed during the five years following CyberKnife SRS for prostate cancer. The primary efficacy goal is to document the rate of biochemical Disease-Free Survival (bDFS), Phoenix and ASTRO definitions, at 5 years.

SECONDARY OBJECTIVES: to measure the following in the study population: Rates of local failure, distant failure, disease-free survival, disease-specific survival, and overall survival; quality of life (QOL) in generic and organ-specific domains; work effort required in treatment planning and delivery of CyberKnife SRS.

Patients will be followed annually to 10 years, to collect additional data for descriptive analysis.

3.0 **DEVICE**

Accuray, Inc. (Sunnyvale, CA), received FDA clearance in July 1999 to provide treatment planning and image guided stereotactic radiosurgery and precision radiotherapy for lesions, tumors and conditions of the brain, base of skull and cervico-thoracic spine, head and neck using the CyberKnife. On August 10, 2001, Accuray, Inc. received 510(k) FDA clearance (510(k) number K011024) to provide treatment planning and image-guided stereotactic radiosurgery and precision radiotherapy for lesions, tumors, and conditions anywhere in the body when radiation treatment is indicated.

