 - 9.4.2 CRITERIA FOR LOCAL FAILURE: clinical evidence of local progression or recurrence. Clinical failure includes a palpable abnormality that has increased in size, failure of regression of a palpable abnormality by 2 years after treatment, or redevelopment of a prostate abnormality after complete response. Patients with a prostate abnormality compatible with local recurrence, or a PSA failure shall undergo a prostate biopsy. Histologic criteria for local failure is a positive prostate biopsy more than 2 years after treatment. Patients with a normal exam and no evidence of PSA failure shall be considered controlled locally. Patients with clinical failure and no biopsy are considered local failures. If a patient is locally

controlled at the time of orchiectomy or androgen ablation, he is censored and considered "not evaluable" for further local control.

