9.4.3 CRITERIA FOR NONLOCAL FAILURE

- 9.4.3.1 DISTANT FAILURE (includes regional failure): documented if clinical, bone scan, CT or other imaging study shows metastatic disease. Biochemical failure with a negative prostate biopsy shall be considered distant only failure. Biopsy of metastatic site required if radiographic or clinical findings are equivocal. Type of metastatic failure (distant and/or regional) shall be recorded if known. Prostate biopsy recommended at this time.
- 9.4.3.2 DISEASE-FREE SURVIVAL: for any measure of disease, including PE, PSA, bone scan, CT/MRI and biopsy, or death.
- 9.4.3.3 DISEASE-SPECIFIC SURVIVAL: for any of the following:
 - 9.4.3.3.1 Death due to prostate cancer.
 - 9.4.3.3.2 Death due to other causes, with active malignancy (defined by clinical or biochemical evidence of progression). If a patient suffered a previous relapse, but has inactive disease, this is not considered a disease-specific death.
 - 9.4.3.3.3 Death due to complications of treatment.
- 9.4.3.4 OVERALL SURVIVAL: for death from any cause

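### Kaplan-Meier alone for local and distant failure implicitly censors deaths, so it modestly overstates the proportion of men who fail, mainly late in the 10-year follow-up

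*Combined protocol and SAP*

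**What the plan says.** The secondary objectives in section 2.0 are "Rates of local failure, distant failure, disease-free survival, disease-specific survival, and overall survival". The same section adds: "Patients will be followed annually to 10 years, to collect additional data for descriptive analysis".

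Section 11.4.2.3 lists the outcomes to be analysed ("These include Local and Distant tumor Control", then disease-free, disease-specific and overall survival) and gives one method for all of them. Kaplan-Meier curves are drawn periodically up to the end of patient follow-up, and "From the Kaplan-Meier curve, descriptive statistics will be calculated including estimates of survival rates and mean and quartile survival times". Neither competing risks nor cumulative incidence is mentioned anywhere in the document.

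The definitions differ in how they treat death. Disease-free survival (9.4.3.2) and overall survival (9.4.3.4) count it as an event. Local failure (9.4.2) and distant failure (9.4.3.1) do not include it, and no text says what happens to a man who dies without either.

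Section 9.4.2 has one explicit censoring rule, for local control only: if a man is locally "controlled at the time of orchiectomy or androgen ablation, he is censored". Section 9.4.3.1 has no such rule for distant failure.

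**The concern.** A man who dies without local failure can never have one. If Kaplan-Meier is the only estimator and death is not an event, he can only be censored, and the curve then treats him as though he would have gone on to fail at the same rate as the men still under observation. One minus that curve describes a setting in which nobody dies. The objective in section 2.0 is the rate of failure, and most readers will take it as the proportion of treated men who fail. For that target 1-KM errs upward, and increasing the sample does not remove the error.

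Deaths accumulate with time, so the error grows over follow-up and is largest in the 10-year figures. What is at stake is the accuracy of the long-term local and distant failure rates.

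**Working it through.** **The plan's own figures.** The documents give no rate for local failure, distant failure, death or androgen ablation, so there is no stated result to reproduce on this point. The cohort size does reproduce: 298 + 21 = 319 (11.2.5), and splitting the 21 in the ratio 1.43:1 gives 12 and 9, so 178 + 12 = 190 low-risk and 120 + 9 = 129 intermediate-risk men.

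**Inputs.** n = 319, 190 or 129 from section 11.2.5, and T = 10 years from section 2.0. Assumed: constant hazards, a death rate λ2 of 1-4% a year, a value F for 1-KM at time T, and no other loss.

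**Formulas.**
- Failure hazard: λ1 = −ln(1 − F)/T
- Cumulative incidence: CI = λ1/(λ1 + λ2) × [1 − exp(−(λ1 + λ2)T)]
- Excess = F − CI
- Greenwood variance of Kaplan-Meier: (1 − F)² × λ1/[n(λ1 + λ2)] × [exp((λ1 + λ2)T) − 1]

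**One case in full.** F = 10%, T = 10, λ2 = 0.02, n = 319.
- λ1 = −ln(0.90)/10 = 0.010536, and λ1 + λ2 = 0.030536.
- CI = 0.3450 × (1 − e^−0.30536) = 0.3450 × 0.2631 = 9.08%.
- Excess = 10.00 − 9.08 = 0.92 points.
- Variance = 0.81 × 0.3450/319 × 0.3571 = 0.000313, so SE = 1.77 points.
- Ratio = 0.92/1.77 = 0.52 SE.

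**10 years, 1-KM of 10%, n = 319.**

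| Deaths a year | Cumulative incidence | Excess (points) | SE (points) | Excess in SE |
|---|---|---|---|---|
| 1% | 9.52% | 0.48 | 1.72 | 0.28 |
| 2% | 9.08% | 0.92 | 1.77 | 0.52 |
| 3% | 8.66% | 1.34 | 1.82 | 0.74 |
| 4% | 8.27% | 1.73 | 1.87 | 0.93 |

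**Other failure levels, same death rates, n = 319.**
- 10 years, 1-KM of 5%: 0.24-0.87 points (0.19-0.64 SE).
- 10 years, 1-KM of 15%: 0.71-2.57 points (0.34-1.16 SE).
- 5 years, 1-KM of 5%: 0.12-0.46 points (0.10-0.36 SE).

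**Smaller n.** At F = 10% and 2% a year the excess stays at 0.92 points, but the ratio falls to 0.46 SE at n = 251 (the 101 + 150 evaluable men of 11.2.1 and 11.2.2), 0.40 at n = 190 and 0.33 at n = 129.

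**Probability of competing death by year 10 at which the excess reaches half an SE.**
- n = 319, no loss: 42%, 33%, 25%, 20%, 17% and 14% for F = 2%, 3%, 5%, 8%, 10% and 15%.
- n = 319, 30% lost by year 10: 19% at F = 10%; with a death hazard that also rises over time, 24%.
- F = 5%, no loss: 33% in the low-risk cohort and 41% in the intermediate-risk cohort.

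**Simulation.** In 4,000 trials of 319 men with F = 10% and a 25% probability of competing death by year 10, mean 1-KM was 10.03% and mean Aalen-Johansen 8.74%. The difference of 1.29 points is 0.72 of the standard deviation of the Kaplan-Meier estimate; the formula gives 0.71.

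**The case against.** The strongest reply is that the size is uncertain and little depends on it. Every rate above is assumed. The nearest figure in the documents, the 97.5% 5-year biochemical disease-free survival expected for low-risk men (11.2.2), suggests few failures. With 2-5% failure at 10 years, half a standard error needs 25-42% competing deaths even in the pooled 319. Eligibility (ECOG 0-1, no other invasive malignancy in 5 years) selects fitter men. Years 6-10 are expressly descriptive, and no test, threshold or stopping rule uses these curves. All of this stands and limits the importance of the point. It does not remove the upward bias. In relative terms the overstatement hardly depends on the failure level: at 2% a year it is 0.92/9.08, about 10%, when 1-KM is 10%, and 0.46/4.54, again about 10%, when it is 5%.

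A second reply is that net tumour control is a legitimate quantity and that censoring at death is inferred, not written. Both are true. But section 2.0 asks for rates of failure, and the plan neither states a net target nor offers another way to handle deaths.

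Three stronger readings are tempting and are not supported:
- A reader might infer that androgen ablation is censored for both endpoints and adds to the overstatement of both. The rule is in 9.4.2 only. For distant failure, 9.4.3.1 says "Biochemical failure with a negative prostate biopsy shall be considered distant only failure", so a man given ablation after that is already an event.
- A reader might infer that ablation censoring must also push local failure upward. Local failure can still occur after ablation, and men who start it are probably at higher risk. If the target is local failure in the absence of ablation, removing them could understate it; if the target is local failure observed before ablation, 1-KM overstates it. The direction depends on a target that the plan does not state.
- A reader might extend the point to disease-specific death. No bias was calculated there, and 9.4.3.3.2 already counts some other-cause deaths as events.

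**Conclusion.** The point holds for deaths. With Kaplan-Meier as the only estimator and death outside both definitions, 1-KM cannot fall below the cumulative incidence, and it exceeds it once any failure follows a censored death. At 10 years, with 1-KM of 10%, constant hazards, 319 men and no other loss, the excess is about 0.5-1.7 points (0.28-0.93 SE) for deaths at 1-4% a year. Half a standard error is therefore reached in some late scenarios only: it needs about 17% competing deaths by year 10 at 10% failure, and more with fewer failures, a single cohort or loss to follow-up. At 5 years the excess is small.

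Nothing here reaches the primary analysis. The efficacy criterion in 11.4.1.2 is a confidence limit on a binomial proportion, and the sample size does not use these curves. Disease-free and overall survival already count death. This is a cheap improvement to descriptive secondary outcomes.

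**What to change.** In section 11.4.2.3:
- State how death without failure is handled for local and for distant failure.
- Report the cumulative incidence (Aalen-Johansen) of each, with death without that failure as a competing event.
- Keep Kaplan-Meier as a supplementary line for comparison with older series, and as the main method for disease-free and overall survival.

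Leave the ablation rule in 9.4.2 in place and add a sensitivity analysis for local failure done two ways: ablation as a competing event, and follow-up continued through ablation. The first counts only failures before ablation. The second depends on what local findings are recorded afterwards, which may be sparse because 9.4.2 treats these men as not assessable for later local control. State which question each version answers.

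The cost is a few sentences and slightly more analysis, with the same data and standard software. The headline failure rates become less directly comparable with older Kaplan-Meier series, which the supplementary line largely offsets.
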